Specific Aims/Purpose: The goal of this single-blinded, randomized control trial is to evaluate and optimize the technique for performing intradetrusor injections of BTX-A for the treatment of idiopathic overactive bladder. We will propose two different reconstitution and injection schema and study patient-centered outcomes related to procedural discomfort and symptom relief.

-Primary Aim: The primary aim of this study is to evaluate perceived discomfort using the Numeric Pain Scale (NPS) during office injection of intradetrusor BTX-A via two different injection techniques and reconstitution volumes.

-Secondary Aims: The secondary aims of this study are to evaluate treatment effectiveness and patient satisfaction of treatment with BTX-A using validated questionnaires. We will also compare procedure time and post-procedure complication rates between the two study groups.

Background

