Urinary urgency, frequency, and urgency incontinence without urinary tract infection are components of a syndrome called overactive bladder (OAB).¹ OAB affects up to 27% of women in the United States and has been shown to negatively impact quality of life and increase rates of depression and sleep disturbances.¹⁻⁴ An algorithmic treatment approach to OAB has been recommended by the American Urological Association (AUA) and includes initiating therapy with conservative measures and behavioral modifications as first line, medication management as second line, and progression to referral for third line treatment including OnabotulinumtoxinA (BTX-A) injections, peripheral tibial nerve stimulation (PTNS), or sacral neuromodulation (SNM).^{5,6} OAB is often refractory to conservative and medication management, with some studies demonstrating good response to medication in 56% and only 50% adherence to oral therapy.^{7,8} Given unsatisfactory treatment response, side effect profile, and the cost of oral medications, more women are moving towards third line options for the treatment of refractory OAB. Injection of intradetrusor BTX-A is a highly efficacious therapy with a reliable safety profile and demonstrable improvements in subjective and objective measures for OAB symptom control.^{4,9,10,11} This procedure is quick and requires limited equipment, making it ideal for the outpatient office setting. Despite BTX-A being a common practice, limited research has been done to optimize injection technique. The industry recommended dose of BTX-A for idiopathic overactive bladder is 100 units¹² and is most often reconstituted in 10 mL delivered in 20 injections (0.5 mL). This reconstitution volume and injection schema were developed arbitrarily and there are wide variations in injection techniques across practitioners. Given the paucity of data for procedural optimization, this study aims to analyze the way intradetrusor BTX-A injections are performed with a focus on the patient-centered outcomes of procedural discomfort and patient satisfaction.

Study Design

Hypothesis: We hypothesize that women undergoing intra-detrusor injection of 100 units of OnabotulinumtoxinA will have less procedural discomfort with a protocol utilizing a lower reconstitution volume and injection number, while still maintaining efficacy of the procedure.

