Design: This will be a single-blinded, parallel randomized control trial (RCT) utilizing two study arms. This trial will be designed and reported as outlined in the CONSORT guidelines.¹³

Recruitment: Female patients scheduled to undergo injection of 100 units of intradetrusor BTX-A for the treatment of idiopathic overactive bladder will be identified through the electronic medical record (EMR). **This is the standard of care/standard dosing for the treatment of OAB and we will recruit and sample from patients who are already scheduled for this therapy prior to study enrollment.** Idiopathic OAB will be defined as “urinary urgency, with or without urgency urinary incontinence, usually accompanied by urinary frequency and nocturia, in the absence of urinary tract infection or other obvious pathology” and without evidence of neurogenic bladder.¹ These patients will be approached on the day of the procedure and consented in person if they are interested in participating.

Study Groups: The patients will be randomized to one of two groups:

- 100 units BTX-A reconstituted in 5 mL normal saline, injected into the bladder in 5 separate injections of 1 mL. One injection will be at the trigone
- 100 units BTX-A reconstituted in 10 mL normal saline, injected into the bladder in 10 separate injections of 1 mL. One injection will be at the trigone

Each of these methods of BTX-A injection into the bladder are considered to be standard of care and are performed routinely in our daily practice.

Randomization:

- Eligible and consenting subjects will be randomized with equal probability of assignment (1:1) to one of the two study arms (5 mL/5 injections vs 10 mL/10 injections). Randomization will occur on the day of the procedure immediately after consent.
- The randomization schedule will be generated using the NIH National Cancer Institute Clinical Trial Randomization Tool. Opaque folders with the study number, consent and envelope-sealed randomized group allocation will be created by the primary co-investigator and will be stored in a locked cabinet. The randomized allocation will be opened by the attending physician after the study consent has been completed and the BTX-A will then be prepared for injection.

Blinding: This will be a single-blind RCT. The patients will be blinded to their treatment allocation but for practical purposes, the attending physician will not be blinded given that they will be performing the injections.

Primary Outcomes:

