1. The primary outcome of this study will be patient discomfort related to BTX-A injection.
2. This will be measured using a validated 11 point (0-10) pain scale – the Numeric Pain Scale (NPS). Patients will rate their discomfort via the NPS prior to and after injections. The measurement for comparison will be the difference in those values.

Secondary Outcomes:

1. Efficacy and patient satisfaction will be evaluated using the Overactive Bladder Symptom and Health-Related Quality of Life Short-Form (OAB-q SF) validated questionnaire.¹⁵ The OAB-q SF is a condition-specific questionnaire developed to assess the symptom bother and health related quality of life (HRQL) impact of OAB. The form asks patients to detail their level of bother related to their bladder symptoms and how those symptoms have affected their lives in the last four weeks. There are 19 questions in total and answers are recorded by checking a box from 1-6. Raw scores are then transferred to a 0-100 scale using formulas provided in the validation literature.¹⁵

2. Procedure time will be recorded from the start of cystoscope insertion to cystoscope removal and procedure end.
3. Symptomatic urinary tract infection (UTI) within the first 30 days after the procedure will be recorded. Symptomatic UTI will be defined as positive nitrites or leukocyte esterase on urine dip or positive urine culture in addition to the presence of dysuria, hematuria, or urinary frequency/urgency in the 30 days after the procedure
4. Rate of bothersome incomplete bladder emptying requiring catheterization within the first 30 days of the procedure
5. Incidence of bleeding requiring admission or hospital/office evaluation related to the injection procedure

Demographic data: collected from the EMR for secondary analyses

1. Age
2. Race
3. Body mass index (BMI)
4. OAB diagnosis at the time of procedure – OAB with vs OAB without urinary incontinence
5. Number of total BTX-A procedures
6. Past medical history
7. Past surgical history
8. Chronic narcotic use
9. 3 or more symptomatic UTI in the last year
10. Anticoagulation use

Sample Size Calculation and Statistical Methods:

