Women scheduled to undergo 100 units intradetrusor BTX-A injections in the office for the diagnosis of idiopathic OAB within the Houston Methodist departments of Urology and Urogynecology	Prior diagnosis of neurological conditions such as cerebral vascular accident within 6 months prior to treatment, Parkinson's Disease, Multiple Sclerosis, myelomeningocele, traumatic neurologic or spinal injury, or a former diagnosis of neurogenic bladder.
18 years of age or older	Symptomatic UTI at the time of procedure, defined as positive nitrites or high-volume leukocyte esterase on urine dip in addition to at least one of the following symptoms: dysuria, gross hematuria, suprapubic pain, frequency/urgency above baseline
Able to give informed consent in English or Spanish	Diagnosis of a bladder pain syndrome or other chronic pain syndromes including fibromyalgia, chronic pelvic pain, pelvic floor dysfunction, levator myalgia
Understand and are willing to undergo follow-up and complete all questionnaires as described in this protocol	Known bladder malignancy
	Previous history of bladder augmentation or reconstructive surgery not related to prolapse
	Pregnancy

Screening and Recruitment

Female patients scheduled to undergo injection of 100 units of intradetrusor BTX-A for the treatment of idiopathic overactive bladder will be identified through the electronic medical record (EMR). A trained, primary member of the research team will identify all patients scheduled for BTX-A as listed on the EPIC schedule for the Urogynecology and Urology providers listed above: [name], , [name], [name], [name], [name], and [name]. Without opening charts, a note can be placed on the schedule for female patients >18 yo to be evaluated for study qualification. The physician caring for the patient on the day of their scheduled BTX-A procedure will identify whether the patient meets inclusion/exclusion criteria for study enrollment based on the criteria listed in this protocol (inclusion and exclusion criteria are listed in the Study Population section above). By this process, the patients' information in the EMR will only be accessed by primary medical team members and will only be accessed by study team members after patients agree to enroll.

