Idiopathic OAB will be defined as “urinary urgency, with or without urgency urinary incontinence, and is usually accompanied by urinary frequency and nocturia, in the absence of urinary tract infection or other obvious pathology” and without evidence of neurogenic bladder.¹ These patients will be approached on the day of the procedure and consented in person if they are interested in participating. Other than a detailed consent form, no recruitment materials or advertisements will be utilized as part of this study.

Withdrawal of Subjects

- Subjects would be withdrawn from the study if they are found to have symptomatic urinary tract infection on the day of the procedure – this would be defined by symptoms such as dysuria, frequency or urgency above baseline, or hematuria along with a urine dip that is positive for nitrites or leukocyte esterase.
- Subjects would be withdrawn if they are not able to tolerate the procedure itself and it is terminated prior to full injection of reconstituted BTX-A or if BTX-A was not able to be injected for other reasons (difficult anatomy, unable to pass scope or perform in the office)

Provisions to Protect the Privacy Interests of Subjects

- Privacy will be protected by ensuring that the patient interacts with and discloses information to only essential members of the research team to maximize confidentiality
 - Caregivers that patients interact with during a typical BTX-A procedure include front desk staff for check in, the nurse/medical assistant helping with the procedure, a resident or fellow if present in clinic that day, and the attending staff.
 - Additional personnel patients would have to interact with to participate in the study would be a research member during the consent process ([name] - Fellow, [name], [name] - research coordinators) and a research member during the telephone follow-up ([name])
- The patient will be made to feel at ease with this research through a thorough explanation of the study protocol, the BTX-A procedure itself, and follow-up telephone encounter. All study members will be introduced by name and title and it will be well-explained that either injection protocol are standard ways that we perform BTX-A in the office every day.

Risks to Subjects

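### The 30-day UTI outcome counts frequency/urgency with no reference level, so persisting OAB symptoms plus a non-infective positive urine test can be recorded as a UTI

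*Combined protocol and SAP*

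**What the plan says.** Secondary Outcomes, item 3, has two limbs. The test limb is a dip positive for nitrites or leukocyte esterase, or a positive culture; any one suffices. The symptom limb is added as "in addition to the presence of dysuria, hematuria, or urinary frequency/urgency in the 30 days after the procedure".

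Recruitment defines the enrolled condition as "urinary urgency, with or without urgency urinary incontinence, usually accompanied by urinary frequency and nocturia", without infection or other evident pathology. The Background says the same: "Urinary urgency, frequency, and urgency incontinence without urinary tract infection are components of a syndrome called overactive bladder".

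The protocol defines symptomatic UTI in two other places, both for the day of the procedure. The exclusion criteria list "frequency/urgency above baseline" among the qualifying symptoms. Withdrawal of Subjects uses "symptoms such as dysuria, frequency or urgency above baseline, or hematuria along with a urine dip that is positive for nitrites or leukocyte esterase". No section supplies a similar qualifier for the 30-day outcome.

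On data sources, the study schema takes UTI since the procedure from the electronic medical record. Encounter 2 is a telephone call at 30 days, with the OAB-q SF repeated and a standardized script. No urine test after the procedure is scheduled.

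On use, Secondary Aims states: "We will also compare procedure time and post-procedure complication rates between the two study groups".

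**The concern.** For a woman whose OAB persists after injection, the symptom limb is already met by the condition being treated. For her, symptomatic UTI reduces to a positive dip or culture, and culture confirmation of a positive dip is not required. The above-baseline qualifier in the two procedure-day definitions shows that the protocol recognises this overlap, yet the only UTI definition that produces outcome data lacks any such qualifier.

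Two things are at stake. First, the recorded UTI rate can be inflated in both arms. Second, a safety outcome becomes linked to residual OAB symptoms. The hypothesis is that the smaller volume and fewer injections will reduce discomfort "while still maintaining efficacy of the procedure", so whether symptoms persist equally in the two arms is a question the trial itself asks. If they do not, the UTI comparison partly reflects efficacy.

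**Working it through.** **1. The plan's own figure.** The only computed figure is the sample size for the primary outcome. Inputs from Sample Size Calculation and Statistical Methods: effect size w = 0.30, 2 degrees of freedom, power 80%, dropout 20%. Alpha is not stated; 0.05 is assumed. With noncentrality N × w², N = 108 gives 108 × 0.09 = 9.72 and power 80.4%. Then 108 / 0.80 = 135, which matches the plan. The UTI outcome does not enter this calculation, and no power is claimed for it.

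**2. The three UTI definitions side by side.**

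| Place | Applies | Frequency/urgency counts when |
|---|---|---|
| Exclusion criteria | procedure day | above baseline |
| Withdrawal of Subjects | procedure day | above baseline |
| Secondary Outcomes, item 3 | 30 days after | present |

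**3. Illustration of size (assumed inputs).** Let p be the true UTI rate. Let f be the share of uninfected women counted only because unchanged OAB symptoms meet the symptom limb and a urine test is positive without infection. Then

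- f = t × l × s, where t is the share of uninfected women tested, l the share of those tests that are positive without infection, and s the share with persisting symptoms and no other qualifying symptom;
- recorded rate = p + (1 − p) × f;
- extra women = 135 × (1 − p) × f, taking all 135 as having record data.

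Risks to Subjects gives UTI as up to 10-30%, varying with definition, so p = 10% and 30% are used. The values of t, l and s are not in the documents; l = 10% to 30% and s = 50% to 90% are assumed.

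| t | f | Recorded, p = 10% | Extra women | Recorded, p = 30% | Extra women |
|---|---|---|---|---|---|
| 0 | 0 | 10% | 0 | 30% | 0 |
| 10% | 0.5% to 2.7% | 10.5% to 12.4% | 0.6 to 3.3 | 30.4% to 31.9% | 0.5 to 2.6 |
| 30% | 1.5% to 8.1% | 11.4% to 17.3% | 1.8 to 9.8 | 31.1% to 35.7% | 1.4 to 7.7 |

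Example: t = 10%, l = 30%, s = 90% gives f = 0.027; 0.10 + 0.90 × 0.027 = 0.1243; 135 × 0.90 × 0.027 = 3.3.

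**4. Effect on the comparison.** With the same f in both arms, the recorded difference is (1 − f) times the true difference. An assumed true difference of 10 points becomes 9.95 points at f = 0.5%, 9.73 at 2.7% and 9.19 at 8.1%.

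With one true rate p but different f, a spurious difference of (1 − p) × (f₁ − f₂) appears. Take p = 10%, l = 30%, and persistence s = 90% in one arm and 50% in the other. At t = 10%, f is 2.7% and 1.5%, and the spurious difference is 0.90 × 1.2 = 1.1 points. At t = 30%, f is 8.1% and 4.5%, and it is 0.90 × 3.6 = 3.2 points.

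**The case against.** The strongest case on the other side is that little will happen in practice. A false count needs an unscheduled urine test, a positive result without infection, and persisting symptoms. If clinicians test mainly when symptoms change, care already applies a baseline filter. The same definition applies to both arms, and equal misclassification barely moves the comparison. Bias needs an efficacy difference that the hypothesis does not expect. A broad safety definition is also a defensible choice, and the protocol acknowledges that UTI rates depend on definition.

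Most of this stands, and it limits the size and severity of the point. It does not remove the gap: the documents are silent on what prompts a test, and no section requires a clinician's diagnosis or adjudication in place of the stated criteria.

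A reader might infer three stronger things that the documents do not support:

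- *That persisting OAB will be recorded as UTI at a material rate.* That needs widespread testing of uninfected women, which no section describes. Only that it can be so recorded is supported.
- *That the trial loses meaningful power for UTI.* No power for UTI is claimed, and any loss rests on invented arm-specific rates.
- *That the above-baseline wording should simply be copied across.* Those definitions apply before treatment. After treatment, a pre-procedure reference would miss a woman whose urgency improved and then returned to its old level during a real infection, which again ties the outcome to efficacy.

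**Conclusion.** The point holds as a minor weakness in the definition. As written, the 30-day UTI outcome can count persisting OAB symptoms with a non-infective positive test as a symptomatic UTI. The documents do not allow the size to be derived, and it may be near zero. With 10% of uninfected women tested and the other assumed ranges above, it is about 0.5 to 3.3 extra women of 135 across true rates of 10% and 30%. With equal misclassification, both rates rise and a true difference shrinks slightly. Only if symptom persistence differs between arms does the comparison partly reflect efficacy, and nothing in the documents shows that it will. The primary outcome and N = 135 are unaffected.

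The exclusion criteria and Withdrawal of Subjects also differ from each other on leukocyte esterase. That concerns the procedure day, needs its own reconciliation, and lends no support here.

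**What to change.** In Secondary Outcomes, item 3, replace the frequency/urgency term with *new or worsened urinary frequency/urgency*. State that the reference is the woman's own symptom level just before the episode, not only her pre-procedure level, so that urgency returning after improvement still counts.

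Apply the rule identically in both arms, from the medical-record entry for the episode and one question added to the existing 30-day telephone script. State in advance that an episode neither source can settle is counted as a UTI. Report the rate under the current protocol wording as a sensitivity analysis.

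The cost is one line of definition, a short written rule and one scripted question, with no added visit or urine test. The downsides are some recall and judgement, and a somewhat lower recorded UTI rate. Symptom level just before an episode is not routinely collected: the OAB-q SF is completed only at Encounter 1 and at 30 days, and it asks about the previous four weeks. The attending physician is unblinded and the documents do not say whether the caller knows the allocation, so the rule should be fixed in writing beforehand. Worsened urgency with a non-infective positive test, and false-positive tests with dysuria or hematuria, would still be counted.

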- The sample size was calculated by powering to the primary outcome of procedural discomfort as rated on the NPS. Cohen effect sizes were used with a power of 80%. The calculation accounted for a potential subject dropout rate of 20%. Three categorical variables (two degrees of freedom) will be utilized – Low discomfort vs. moderate discomfort vs. high discomfort – with a Chi-squared statistical analysis.
- Utilizing the above methods and an effect size of 30%, our target sample size will be 135 patients in total split between the two study groups.
- Variables will be defined as following on the NPS:
 - Low discomfort – 0-2
 - Moderate discomfort – 3-6
 - High discomfort – 7-10

Standard Practices and Considerations based on FDA recommendations for BTX-A:

1. Antiplatelet medications will be held for 72 hours prior to the procedure and can be restarted on the day after injection
2. Antibiotic prophylaxis will be prescribed for the day before, day of, and day after the procedure

Encounter 1

Scheduled visit for 100 units
intradetrusor BTX-A

10 mL/10 injections
vs.
5 mL/5 injections

- Consent obtained and patient completes OAB-qSF
- Randomization → Reconstitution of BTX-A in 10 mL vs 5 mL (patient blinded) → Patient rates discomfort from 0-10 on NPS → BTX-A injected → patient rates discomfort from 0-10 on NPS

Encounter 2

Telephone call at 30 days post
procedure

[figure not shown]
Data Collected from EMR:

- Demographic data → Age, Race, BMI, PMH, PSH, narcotic use, recurrent UTI, anticoagulation use
- Procedural data → UTI since procedure, Urinary retention requiring catheterization

- OABq-SF completed again
- Overall satisfaction since procedure assessed via standardized telephone script

Study Intervention

- The patients will be randomized into one of two treatment groups. In each of these groups, a different volume of normal saline will be used to reconstitute (dissolve) the BTX-A. The same injection volume (1 mL) will be utilized between groups, leading to a different number of total injections between groups
- Group A: 100 units BTX-A reconstituted in 5 mL normal saline, injected into the bladder in 5 separate injections of 1 mL. One injection will be at the trigone
- Group B: 100 units BTX-A reconstituted in 10 mL normal saline, injected into the bladder in 10 separate injections of 1 mL. One injection will be at the trigone

- Anatomic definitions:
 - Ureteral orifice: opening of ureter into the bladder

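### The only named primary analysis puts the 0-10 NPS into three unordered bands, which costs power and gives no estimate in NPS points

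*Combined protocol and SAP*

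**What the plan says.** Primary Outcomes, item 2, names the 11-point (0-10) Numeric Pain Scale, has patients rate discomfort before and after the injections, and then states: "The measurement for comparison will be the difference in those values". That describes a numeric change.

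Sample Size Calculation and Statistical Methods names one analysis for this outcome: "Three categorical variables (two degrees of freedom) will be utilized – Low discomfort vs. moderate discomfort vs. high discomfort – with a Chi-squared statistical analysis". The bands are "Low discomfort – 0-2", "Moderate discomfort – 3-6" and "High discomfort – 7-10". The same section gives 80% power, an effect size of 30%, 20% dropout and a total of 135 patients.

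No t-test, rank test, ordinal model or covariate-adjusted model of the ungrouped score is named. The plan does not give a reason for the cut-points, a significance level, an expected NPS mean or SD, or expected band proportions. It also does not say whether the bands apply to the post-injection rating or to the difference.

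**The concern.** The hypothesis in Study Design is directional: less discomfort with fewer injections and a lower volume. It predicts a shift along the scale. The planned test uses that information poorly in two ways.

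- **Banding.** A score of 3 and a score of 6 count as the same, while 2 versus 3 counts as a full category change.
- **Order.** A 2-df chi-squared test treats the three bands as unordered labels. A move from high to low is not recognised as going further than a move from high to moderate.

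The test also gives a p-value and a table of proportions, but no difference in NPS points with an interval, which is what Primary Outcomes leads the reader to expect. A real reduction could be missed although the ratings that would show it have been collected.

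**Working it through.** **1. Reproduce the plan's sample size.** Inputs from Sample Size Calculation and Statistical Methods: 2 df, effect size 30% read as Cohen w = 0.30, power 80%, dropout 20%. Alpha is not stated; 0.05 is assumed.

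- Noncentrality = N × w² = 108 × 0.09 = 9.72. A noncentral chi-squared with 2 df then gives 80.4% power.
- Inflation for dropout: 108 / (1 − 0.20) = 135, which matches the plan exactly.

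**2. Compare tests at that same effect.** There were 54 evaluable patients per arm and 20,000 simulated trials per scenario. Because the documents give no NPS distribution, two families on 0-10 were assumed: a rounded normal (mean 2.5-6, SD 2-3) and a skewed beta-binomial (mid-point mean 2-5). In each, the arms were shifted in one direction until the three bands gave w = 0.30. Power in %:

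| Assumed scores | Chi-squared, 3 bands | Rank test, same bands | Wilcoxon, 0-10 | t-test, 0-10 |
|---|---|---|---|---|
| Rounded normal, mean 4, SD 2.5, shift 1.78 | 82.1 | 88.7 | 94.3 | 94.7 |
| Beta-binomial, means 3.20 and 4.86 | 82.4 | 89.1 | 93.1 | 93.6 |
| Beta-binomial, means 1.37 and 2.82 | 82.0 | 89.3 | 97.4 | 96.5 |

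**3. Split the gain, using the Wilcoxon column.**

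- Row 1: order 88.7 − 82.1 = 6.6; banding 94.3 − 88.7 = 5.6; total 12.2 points.
- Row 2: order 89.1 − 82.4 = 6.7; banding 93.1 − 89.1 = 4.0; total 10.7 points.
- Row 3: order 89.3 − 82.0 = 7.3; banding 97.4 − 89.3 = 8.1; total 15.4 points.

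Over all scenarios run, the total gain is about 10-18 points, of which about 4-9 are due to the banding.

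**4. A smaller, fixed shift.** For 1 NPS point (mean 3-5), power for the planned test, the rank test on the bands and the full scale is 44-48%, 57-60% and 69-70% at SD 2. At SD 2.5 it is 32-36%, 41-45% and 50-52%.

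**5. Which full-scale value is analysed.** The w = 0.30 scenarios correspond to about 0.7 SD on the post-injection score (for example 1.78 / 2.5 = 0.71). Approximate power is Φ(d√(n/2) − 1.96) with n = 54. Assume equal pre- and post-injection SD and correlation ρ.

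- Unadjusted difference: d = 0.7 / √(2(1 − ρ)). At ρ = 0, d = 0.495 and power is 73%. At ρ = 0.3, d = 0.592 and power is 87%. At ρ = 0.5, d = 0.70 and power is 95%.
- Post-injection score with baseline as covariate: d = 0.7 / √(1 − ρ²). Power is 95% at ρ = 0, 97% at ρ = 0.3 and 99% at ρ = 0.5.

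Simulations of the unadjusted difference at zero correlation gave about 72-79%. So the gain depends on how the pre-injection rating is used.

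**The case against.** Low, moderate and high discomfort is a prespecified endpoint that clinicians can read, and the trial keeps its planned 80% power at w = 0.30. That no guideline requires these cut-points does not make them wrong. All of this stands, and it limits the point to efficiency and interpretability.

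A reader might charge the whole power loss to the banding. The split above does not support that: a rank test on the same three bands already recovers roughly half of it.

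A reader might also infer that a shift of 1-2 points is hidden from the planned test. It is not. A 1.78-point shift at SD 2.5 gives the chi-squared test 82.1% power. Near 1 point it is weak, but there the full scale also falls short of 80%. The documents do not say what shift is expected.

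The strongest objection is that the simulations use a single 0-10 score, whereas Primary Outcomes names the difference. If the unadjusted difference is analysed and the two ratings are nearly uncorrelated with equal spread, its power can drop below that of the chi-squared test on post-injection bands. This stands. Banding that same difference would do worse still, so the like-for-like direction is unchanged, but the remedy must say which value is analysed and how baseline enters.

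Finally, the gain needs a shift in one direction. If the arms differed mainly in spread, the chi-squared test could be the better one. The stated hypothesis is directional, so this is a limit and not a rebuttal.

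**Conclusion.** The point holds as one of lost efficiency and interpretability, and it should be addressed. The plan collects a 0-10 score twice and defines a numeric comparison, then tests three unordered bands. At the plan's own effect size, a full-scale comparison would gain about 10-18 points of power, about 4-9 from undoing the banding and the rest from using order. It would also supply an estimate in NPS points.

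These figures rest on alpha 0.05, 108 evaluable patients, a one-directional shift and assumed NPS distributions. None of the four is a sponsor-stated figure, except that 108 follows from 135 and the 20% dropout. The advantage is not assured for an unadjusted difference score when the pre-post correlation is near zero.

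A reader might conclude that the trial is underpowered or wrongly sized. The documents do not support that: 135 reproduces exactly for the test that was chosen.

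**What to change.** In Sample Size Calculation and Statistical Methods:

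- **Primary analysis.** Use a linear model (ANCOVA) of the ungrouped post-injection NPS on arm, with the pre-injection NPS as covariate. Report the adjusted between-arm difference in NPS points with a 95% CI. Modelling the pre-post difference with the same covariate gives an identical arm effect, so this agrees with Primary Outcomes, item 2.
- **Bands.** Keep the Low/Moderate/High table as a secondary summary and state which NPS value it bins. The bands cover 0-10, whereas a difference can be negative.
- **Sample size.** Keep N = 135, state alpha, and note that the number was derived for the three-category test. Do not describe it as conservative for an unadjusted difference score, whose power may be only about 72-79%.
- **Timing.** Make the change before outcome data are examined.

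The cost is a few sentences. No patients, visits or data are added, because both ratings are already collected. The downside is that the category result moves from primary to secondary.

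### The only primary test, a 2-df chi-squared, ignores the order of the discomfort categories, so significance need not mean less discomfort, and no estimate, confidence interval or direction is specified

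*Combined protocol and SAP*

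**What the plan says.** Under Study Design, the hypothesis is that women treated with 100 units "will have less procedural discomfort with a protocol utilizing a lower reconstitution volume and injection number". Under Primary Outcomes, the quantity compared is the change in the 0-10 NPS rating from before to after the injections; no test is named there.

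Under Sample Size Calculation and Statistical Methods, the plan states that "Three categorical variables (two degrees of freedom) will be utilized", and describes the analysis as "Low discomfort vs. moderate discomfort vs. high discomfort – with a Chi-squared statistical analysis". The bins are 0-2, 3-6 and 7-10. The same section gives the sizing: "Cohen effect sizes were used with a power of 80" per cent, "an effect size of 30" per cent, and "our target sample size will be 135 patients in total split between the two study groups", with 20% allowed for dropout. Allocation is 1:1. Alpha and the expected proportions in each category are not stated.

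The plan names no trend test, rank test, ordinal model, effect measure, confidence interval or rule for direction.

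**The concern.** Two degrees of freedom in a 2x3 table identify the general-association chi-squared. It treats Low, Moderate and High as three names: exchanging the labels Moderate and High leaves the p-value unchanged. It responds to any difference in shape between the arms, including one where the gain in Low is cancelled by a gain in High.

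The question asked is whether one technique hurts less. A p-value from this test does not answer it alone, and the plan provides nothing alongside it that would. The direction and size of the effect would be read from the table after the fact, with freedom to stress whichever category happened to differ. Part of the test's sensitivity is also spent on patterns that the hypothesis does not concern.

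**Working it through.** **Inputs.** From the plan: 2 df, 80% power, effect size 30% (read as Cohen's w = 0.30), 20% dropout, 135 in total, 1:1. Assumed: alpha 0.05, and all category proportions below.

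**1. The plan's own figure.** Noncentrality = N × w². With 2 df and a critical value of 5.991, 80% power needs a noncentrality of 9.635, so N = 9.635 / 0.09 = 107.05, rounded up to 108. Then 108 / (1 − 0.20) = 135, which matches. Alphas of 0.10, 0.025 and 0.01 give 108, 160 and 194 instead, so 0.05 is a reasonable assumption.

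**2. Ordered test on the same bins, best case.** If all of the effect lies on the ordered trend, the same noncentrality falls on 1 df (critical value 3.841).

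| Evaluable | Noncentrality | Power, 2 df | Power, 1 df | Gap |
|---|---|---|---|---|
| 108 | 108 × 0.09 = 9.72 | 80.4% | 87.7% | 7.3 points |
| 135 | 135 × 0.09 = 12.15 | 88.7% | 93.6% | 4.9 points |

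In this case the 1-df test reaches 80% with 88 evaluable (88 / 0.8 = 110 with dropout).

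**3. How far the gain depends on the pattern.** Simulation used 54 per arm, 40,000 runs and six assumed pooled splits, from equal thirds to 60/30/10 and including 20/50/30, each scaled to w = 0.30.

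| Pattern | Chi-squared | Ordered tests on the bins |
|---|---|---|
| Proportional-odds shift | about 82% | 87-89% |
| Low and Moderate exchange only | 82-83% | 34-71% |
| Moderate and High exchange only | 82-86% | 10-53% |
| Moderate gains from both ends | about 82% | 5-10% |

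The ordered test is ahead only if the trend carries more than about 82% of the noncentrality.

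**4. Significance without less discomfort.** Take Low/Moderate/High of 30/50/20 in one arm and 45/22/33 in the other. Scored 0, 1, 2, the means are 0.50 + 0.40 = 0.90 and 0.22 + 0.66 = 0.88: almost no net shift. The pooled split is 37.5/36/26.5, so w² = 0.075²/0.375 + 0.14²/0.36 + 0.065²/0.265 = 0.0854 and w = 0.29, close to the plan's 0.30. At 54 per arm the chi-squared rejects in 80% of trials, an equal-score trend test in 5% and a rank test in 6%. Among the significant chi-squared results, the mean category is higher in one arm in 54% and in the other in 42%; the rest tie.

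**5. Unbinned score.** Illustration only, because the plan gives no score distribution: rounded normal ratings limited to 0-10, SD 2.5, mean 3 or 4, shifted down by 1.25 or 1.5 points, 54 per arm. A rank test on the score had about 19 to 22 points more power than the chi-squared on the bins. Over a wider set of assumptions (means 3 to 5, SD 2 or 2.5, shifts 1 to 1.5) the gain ran from about 12 to 24 points.

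**The case against.** The plan is coherent on its own terms. Test, degrees of freedom, effect size and N agree, and the trial delivers the power it states. That stands: a reader might infer that the trial is underpowered, and the arithmetic shows that it is not.

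A reader might also infer that 7 points are lost whatever the effect, or that the second degree of freedom buys nothing. The documents support neither. They give no category proportions, and the hypothesis does not say that discomfort shifts evenly across the scale. Fewer patients with high discomfort, with Low unchanged, is still less discomfort. With 35/45/20 against 35/62/3, the chi-squared has 79% power and ordered tests on the bins 20-28%. With 30/50/20 against 57/23/20, it is about 82-83% against 46-56%. On the bins, then, the choice is a trade-off.

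The counter-example in step 4 is constructed: it needs the arm with more Low also to have more High, and nothing in the plan suggests that. It shows what the test permits, not what is likely. Direction can be read from a two-arm table, and under consistent shifts (50/40/10 against 70/27/3; 40/45/15 against 67/28/5) no significant result pointed the wrong way. The Design paragraph also commits to CONSORT reporting. These points soften the concern. They do not supply a prespecified estimate, interval or rule for direction, and the missing estimate matters under every pattern.

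**Conclusion.** The point holds as a mismatch between an unordered test and a directional hypothesis, with no effect measure to bridge the two. It is not a shortfall in power or an invalid test.

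The efficiency forgone by ignoring order on the bins is at most about 7 points. That figure rests on w = 0.30, alpha 0.05 (assumed), 108 evaluable and a consistent shift across both cut-points; with all 135 evaluable it is 4.9 points. For a change confined to one cut-point the sign reverses, and the loss from an ordered test on the bins can exceed 50 points. This is why the remedy should use the unbinned measure rather than a trend test on three bins. The gain from unbinning looks larger, but it rests wholly on assumed score distributions.

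**What to change.** In Sample Size Calculation and Statistical Methods, replace the chi-squared as the primary analysis with a two-sided ordered test, at a stated alpha, on the measure that Primary Outcomes defines: the unbinned pre-to-post NPS difference, which can run from −10 to +10. Wilcoxon-Mann-Whitney or a proportional-odds model would serve. Report the common odds ratio, or the mean or median difference, with a 95% CI and a statement of which arm it favours. Show the Low/Moderate/High table by arm as description. Keep 135 patients, and say that this number was derived for the chi-squared on the bins.

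The cost is a few sentences. Both ratings are already collected, so no visit, patient or data item is added. The downside should be stated in the plan: an ordered test is less sensitive to non-monotone differences, and if it is run on the three bins instead, it can lose substantial power when the change is confined to one cut-point.
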